**Iron Endpoints**

TID

21

**Standardized Baseline IV Iron Dose (mg/month)**

- In order to calculate the baseline average monthly IV iron dose, the dose of IV iron will be standardized to obtain a continuous single unit IV iron dose in terms of mg/month for the period from 12 weeks before the Randomization date to the day before the Randomization date.
- IV iron therapy concomitant medication records that occur or are ongoing during the period from (the Randomization date – 12 weeks) to the day before the Randomization date will be selected and ordered by start and end date.
- The standardization will be carried out with the following formula:
  - Standardized IV iron dose (mg/week) = IV iron drug dose (mg) \* frequency

Note: Frequency and Gap Factors defined as follows:

Frequency (from eCRF)	Frequency (for standardization formula)	Gap Factor
2 times per week	2	2.5 days
3 times per week	3	1.33 days
4 times per week	4	0.75 day
5 times per week	5	0.4 day
BID	14	0 days
Once daily	7	0 days
One time dose	1	n/a
Every 12 Hours	14	0 days
Every 2 weeks	0.5	13 days
Every 4 weeks	0.25	27 days
Once a month	0.23	29 days
Once a week	1	6 days
TID	21	0 days

- If the frequency of the record is not 'one time dose', then duration is calculated as follows:
  - If the concomitant medication record start date  $\geq$  Randomization date, the duration of the record is 0.
  - If the concomitant medication record end date + gap factor  $<$  (Randomization date – 12 weeks), the duration of the record is 0.
  - If the concomitant medication record end date + gap factor  $\geq$  (Randomization date – 12 weeks) or the record is ongoing, the duration of the record will be calculated as Stop Date – Start Date + 1 day where:
    - Start date will be the latest of (concomitant medication record start date and the (the Randomization date – 12 weeks)).
    - Stop date will be the earliest of (concomitant medication record stop date + gap factor and the day before randomization).
- If the frequency of the record is 'one time dose', then:

**Iron Endpoints**

- If concomitant medication record start date < Randomization date - 12 weeks, or if Randomization date ≤ concomitant medication record start date, then duration of the record is 0.
- If Randomization date -12 weeks ≤ concomitant medication record start date < Randomization date, then:
  - Frequency (for standardization formula) = 1
  - Duration = 7 days
- The total dose for each IV iron record will be: Standardized dose\*duration/7 days
- A weighted mean will then be used to obtain the baseline monthly IV iron dose:  
Mean baseline monthly IV iron dose = [(IV iron total doseRecord 1) + ... + (IV iron total doseRecord n)] / [(12\* 7)/30.4375 days].

**Standardized IV Iron Dose (mg/month) from Randomization to Week 52**

- In order to calculate the average monthly IV iron dose from Randomization to Week 52, the dose of IV iron will be standardized to obtain a continuous single unit IV iron dose in terms of mg/month for the period from the Randomization date to the Week 52 visit date while the subject is on treatment.
  - Note: Subjects who are randomized but never treated will not have a value for average monthly IV iron from Randomization to Week 52.
- IV iron therapy concomitant medication records that occur or are ongoing during the period from the subject's (Randomization date – 12 weeks) to the Week 52 visit date will be selected and ordered by start date and end date.
- The standardization will be carried out with the following formula:
  - Standardized IV iron dose (mg/week) = IV iron drug dose (mg) \* frequency

Note: Frequency and Gap Factors defined as follows:

Frequency (from eCRF)	Frequency (for standardization formula)	Gap Factor
2 times per week	2	2.5 days
3 times per week	3	1.33 days
4 times per week	4	0.75 day
5 times per week	5	0.4 day
BID	14	0 days
Once daily	7	0 days
One time dose	1	n/a
Every 12 Hours	14	0 days
Every 2 weeks	0.5	13 days
Every 4 weeks	0.25	27 days
Once a month	0.23	29 days
Once a week	1	6 days
TID	21	0 days

- If the frequency of the record is not 'one time dose', then duration is calculated as follows:

CONFIDENTIAL

204837

**Iron Endpoints**

- If the concomitant medication record start date > earliest of (treatment stop date + 1 and Week 52 visit date), the duration of the record is 0.
- If the concomitant medication record end date + gap factor < Randomization date, the duration of the record is 0.
- If the concomitant medication record end date + gap factor  $\geq$  Randomization date or the record is ongoing, the duration of the record will be calculated as Stop Date – Start Date +1 day where:
  - Start date will be the latest of (concomitant medication record start date, randomization date, treatment start date).
  - Stop date will be the earliest of (concomitant medication record stop date + gap factor, treatment stop date + 1, and the Week 52 visit date).
- If the frequency of the record is 'one time dose', then:
  - If concomitant medication record start date < treatment start date, or if earliest of (treatment stop date + 1 and Week 52 visit date) < concomitant medication record start date, then duration of the record is 0.
  - If latest of (Randomization date, treatment start date)  $\leq$  concomitant medication record start date  $\leq$  earliest of (treatment stop date + 1 and Week 52 visit date), then:
    - Frequency (for standardization formula) = 1
    - Duration = 7 days
- The total dose for each IV iron record will be: Standardized dose\*duration/7 days
- A weighted mean will then be used to obtain the monthly IV iron dose from Randomization to Week 52:  
 Mean monthly IV iron dose from Randomization to Week 52 while on treatment =  

$$\frac{[(IV \text{ iron total dose}_{\text{Record } 1}) + \dots + (IV \text{ iron total dose}_{\text{Record } n})]}{[\{\text{earliest of (treatment stop date + 1, Week 52 Visit Date)} - \text{treatment start date} + 1\} / 30.4375 \text{ days}]}$$

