**7.2.5.1. Statistical Methodology Specification**

Endpoint / Variables

 
• Average monthly IV iron dose (mg)/participant to Week 52
 

Model Specification

 
• Average monthly IV iron dose (mg)/participant to Week 52 will be determined by calculating the total IV iron dose per subject from Day 1 to Week 52 while the participant was on study treatment and dividing by (the number of days the participant was on study treatment/30.4375 days). See Section 14.4.1 for the definition of on-treatment IV iron.
 
• An ANCOVA model will be used to compare the difference in average monthly IV iron dose per participant between arms, adjusting for: 
 
○ Treatment
 
○ Baseline monthly IV iron dose (see Section 5.2.1)
 
○ Region (as randomized, see Section 5.3 & Section 5.4.1)
 
 
 

Model Results Presentation

 
• The number and percentage of subjects with baseline IV iron use, on-treatment EP IV iron use, and on-treatment IV iron use to Week 52 will be summarized by treatment. Boxplots by study treatment will be created separately for on-treatment average monthly IV iron dose to week 52 and for post-randomization average monthly IV iron dose to week 52.
 
• Average monthly IV iron dose at baseline, while on treatment during the EP, and while on treatment to Week 52 will be summarized by treatment group using mean, standard deviation, minimum, P25, median, P75, and maximum.
 
• The least square (LS) mean estimates and standard errors by treatment group, LS mean difference, two-sided 95% CI and one-sided superiority p-value for the difference in average monthly IV iron dose/subject to Week 52 between the daprodustat and rhEPO arms from the ANCOVA model will be presented. The number of subjects contributing to the analysis and the associated mean and standard deviation of the baseline and Week 52 values will also be displayed with the results of the ANCOVA model.
 
• A listing of average monthly IV iron dose will be provided including treatment, site ID, unique subject ID, subject ID, time period, and average monthly IV iron dose at Week 52.
 

Model Results Interpretation

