**Demographics & Baseline Characteristics**

- If the concomitant medication record start date  $\geq$  Randomization date, the duration of the record is 0.
- If the concomitant medication record end date + gap factor  $<$  Week -4 visit date, the duration of the record is 0.
- If the concomitant medication record end date + gap factor  $\geq$  Week -4 visit date, the duration of a record will be calculated as Stop Date – Start Date +1 day, where:
  - Start date will be the latest of (concomitant medication record start date and the Week -4 visit date).
  - Stop date will be the concomitant medication record end date + gap factor.
- If the frequency of the record is 'one time dose', then:
  - If the concomitant medication record start date  $\geq$  Randomization date, the duration of the record is 0.
  - If Week -4 visit date  $\leq$  concomitant medication record start date, then:
    - Frequency (for standardization formula) = 1
    - Duration = 7 days
  - If concomitant medication record start date  $<$  Week -4 visit date, then:
    - Frequency (for standardization formula): 7/ [earliest of (the day before the next sequential prior ESA concomitant medication record start date and the day before randomization) – start date of record + 1 day]
    - If the earliest non-missing date of (the day before the next sequential prior ESA concomitant medication record start date and the day before randomization)  $<$  Week -4 visit date, the duration of the record is 0.
    - If the earliest non-missing date of (the day before the next sequential prior ESA concomitant medication record start date and the day before randomization)  $\geq$  Week -4 visit date, the duration of the record is calculated as Stop Date – Start Date + 1, where:
      - Start date will be the Week -4 visit date.
      - Stop date will be the earliest of (the day before the next sequential prior ESA concomitant medication record start date and the day before randomization)
- The total dose for each prior ESA record will be: Standardized dose\*duration/7days
- A weighted mean will then be used to obtain the prior ESA dose:  
 Mean prior ESA dose = [(ESA total doseRecord 1) + ... + (ESA total doseRecord n)]/[( Randomization Date – Week -4 Visit Date)/7days]

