**Standardized IV Iron Dose (mg/week) to Determine Iron Management Action**

- In order to compare between IV iron records, to determine the action taken with IV iron therapy in the 8 weeks following the date the IV management threshold was met, the dose of IV iron in each associated record will be standardized in terms of mg/month.
- IV iron therapy concomitant medication records that occur or are ongoing during the 8 weeks following the date the IV management threshold was met (inclusive), will be selected and ordered by start and end date.
  - If there is a record has a start date on the date the IV management threshold was met, and a prior record has an end date on the day before the IV management threshold was met, this prior record will be selected and considered as well.
- The standardization will be carried out with the following formula:
  - Standardized IV iron dose (mg/week) = IV iron drug dose (mg) \* frequency

Note: Frequency defined as follows:

Frequency (from eCRF)	Frequency (for standardization formula)
2 times per week	2
3 times per week	3
4 times per week	4
5 times per week	5
BID	14
Once daily	7
One time dose	1
Every 12 Hours	14
Every 2 weeks	0.5
Every 4 weeks	0.25
Once a month	0.23
Once a week	1

CONFIDENTIAL

204837

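### The IV iron derivation adds a gap factor with no cut at the next record, so it can overstate the principal secondary endpoint, and it credits some pre-randomization iron to on-treatment use

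*SAP*

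**What the plan says.** SAP 7.2.5.1 defines the principal secondary endpoint by "calculating the total IV iron dose per subject from Day 1 to Week 52 while the participant was on study treatment", divided by months on treatment. SAP 7.2.4 also limits it to iron use up to treatment discontinuation, and SAP 14.4.1.1 counts iron as on-treatment only when dated after treatment start.

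SAP 14.6.3.2 gives the derivation. For recurring records:

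- Start: "Start date will be the latest of (concomitant medication record start date, randomization date, treatment start date").
- Stop: "Stop date will be the earliest of (concomitant medication record stop date + gap factor, treatment stop date + 1, and the Week 52 visit date").
- Records that ended earlier: "If the concomitant medication record end date + gap factor < Randomization date, the duration of the record is 0". A record that ended before randomization therefore still counts if its extension reaches randomization.

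Each record's total is dose times frequency times duration over 7 days, and record totals are added. One-time doses are handled differently: the clause opening "If concomitant medication record start date < treatment start date, or if earliest of" gives those dated before treatment start zero duration.

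The baseline and Week 28 to 52 averages use the same extension, also with no cut at the next record. In the same section, the rule for classifying iron management action covers the case where one record starts on a given day and "a prior record has an end date on the day before the IV management threshold was met, this prior record will be selected" as well.

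**The concern.** Suppose one iron record closes and another opens at once, for example after a dose change. The extension then counts the old dose over days on which the new dose is already being counted. Whether milligrams are overstated depends on what the end date means, and the documents do not define it for iron.

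The second issue is a mismatch between definition and derivation. A recurring record that ended before randomization can contribute to a total defined as iron given from Day 1 on treatment. The same infusion coded as a one-time dose contributes nothing.

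This endpoint carries the only multiplicity-controlled superiority test (SAP 5.5). Handovers occur after randomization and follow iron management driven by ferritin and TSAT (Protocol 7.8.1). Protocol 3.3.2 suggests that daprodustat may improve iron availability, so unequal handover counts by arm are possible, though not shown.

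**Working it through.** **Inputs (SAP 14.6.3.2).** Duration = stop − start + 1. Record total = dose × frequency × duration / 7. Frequency and gap factor: weekly 1 and 6 days; every 2 weeks 0.5 and 13; every 4 weeks 0.25 and 27. One month is 30.4375 days.

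**1. Reproducing the gap factors.** Gap = 7/frequency − 1 gives 7/1 − 1 = 6, 7/0.5 − 1 = 13 and 7/0.25 − 1 = 27, as stated. Monthly gives 29.4 against 29. A record holding one dose is credited frequency × (1 + gap)/7 = 1.00 dose for these three schedules. The gap factor completes the interval after the last dose, so it is right when the end date is that dose.

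**2. One handover: 100 mg weekly on days 1, 8, 15 and 22 (true total 400 mg).**

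| Recorded end | Next record starts | As written | With the proposed fix |
|---|---|---|---|
| Day 22 (last dose) | Day 29 | 28/7 × 100 = 400 | 400 |
| Day 28 | Day 29 | 34/7 × 100 = 485.7 | 28/7 × 100 = 400 |
| Day 29 | Day 29 | 35/7 × 100 = 500 | 28/7 × 100 = 400 |
| Day 22 (last dose) | Day 23 | 28/7 × 100 = 400 | 22/7 × 100 = 314.3 |

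**3. Excess per handover when the record closes the day before the next.** Frequency × gap / 7: weekly 6/7 = 0.86 dose; every 2 weeks 0.5 × 13/7 = 0.93; every 4 weeks 0.25 × 27/7 = 0.96.

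**4. Over 52 weeks.** Each regimen below totals 2,600 mg in 364 days: 2,600/(364/30.4375) = 217 mg/month. Four adjoining records (an assumption) make three handovers.

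- 50 mg weekly: 3 × 0.857 × 50 = 129 mg, giving 228 mg/month (+5%).
- 100 mg every 2 weeks: 3 × 0.929 × 100 = 279 mg, giving 241 (+11%).
- 200 mg every 4 weeks: 3 × 0.964 × 200 = 579 mg, giving 266 (+22%).

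Two records give 2% to 7%; six give 8% to 37%. Six records need five changes, against four scheduled on-treatment iron assessments before Week 52 (Protocol Table 1), so that is an outer case.

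**5. Carry-in.** Take a 200 mg every-4-weeks record ending the day before Day 1, with no iron afterwards. Days 1 to 27 count: 0.25 × 200 × 27/7 = 193 mg. Over 52 weeks this is 193/(365/30.4375) = 16 mg/month. If treatment stops at Week 12 it is 193/(86/30.4375) = 68 mg/month. The amount given on treatment is zero. Carry-in is always under one dose per record.

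**6. The opposite boundary.** A 100 mg every-4-weeks dose given 10 days before treatment stop counts for 12 days: 0.25 × 100 × 12/7 = 42.9 mg. A steady 100 mg weekly regimen running through both boundaries gives (100 × 365/7)/(365/30.4375) = 434.8 mg/month, exactly 100 × 30.4375/7.

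**7. Negative duration.** If treatment starts after randomization and the extended stop falls between them, two days before treatment start, then stop − start + 1 = −2 + 1 = −1 day.

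**The case against.** The strongest defence is that Protocol 7.7 asks for start and end dates of administration. Read as the last dose, that makes the rule exact, even where days overlap. The iron-action clause is conditional, serves another purpose and uses no gap factor. The prior-ESA rule that looks to "the day before the next sequential prior ESA concomitant medication record start date" applies only to one-time doses; recurring ESA records get the same uncut extension, so the convention is consistent. Carry-in is proration of a dosing interval: the baseline average stops the day before randomization, so no day counts in both periods, and the cut at treatment stop works the other way.

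Much of this stands. A reader might infer that the endpoint is misstated as planned; the documents do not support that, because under last-dose dating the excess is zero. A reader might also infer that carry-in pulls a true reduction towards zero. It does not: it arises from iron given before randomization, so its expected milligrams are equal in both arms, and a common addition leaves a difference in means unchanged. Unequal time on treatment could alter the monthly figure, but none is shown.

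The dating defence is not conclusive. The Protocol 7.7 wording does not separate a last dose from a regimen end. The SAP convention that medication is taken on its recorded stop date (14.4.1.5) excludes IV iron dose endpoints by its title. Partial stop dates are imputed to the end of the month or to December (14.7.2.1), and these are not known last doses. For in-center iron given weekly or less often, an end date the day before the next start is more plausibly a regimen end. The proration argument holds for steady regimens, not for participants who stop iron at randomization.

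**Conclusion.** The concern holds in a limited form. The rule is correct for last-dose dating and overstates by 0.86 to 0.96 dose per handover for weekly to every-4-weeks records closed the day before the next. Under the assumed four records that is 5% to 22% of a participant's annual average. The percentages rest on a constant dose and an assumed record count. The documents do not give the real count or show a difference by arm, so neither the size nor the direction of any effect on the treatment comparison can be stated.

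Carry-in is a real mismatch between SAP 14.6.3.2 and SAP 7.2.4, 7.2.5.1 and 14.4.1.1. It is under one dose per record, is expected to balance between arms and mainly adds noise, most where treatment is short. Both issues merit correction before unblinding.

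**What to change.** 1. When another IV iron record starts on a record's stop date or the next day, do not add the gap factor, and end the earlier record no later than the day before the new start. Otherwise keep the gap factor. Apply this to the baseline, Week 52 and Week 28 to 52 averages.
2. Floor every record's duration at zero.
3. State in SAP 7.2.4 and 7.2.5.1 that doses at the boundaries are prorated, so that these sections and 14.4.1.1 agree with 14.6.3.2. State also what an iron record's end date means.
4. Add a sensitivity analysis leaving out recurring records that ended before treatment start.

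Counting administrations from nominal intervals is not a safe substitute: weekly doses on days 1, 8, 15 and 20 give floor(19/7) + 1 = 3 instead of 4.

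The cost is SAP wording and a small program change before unblinding, with no new data. It departs from the derivation text used so far. It also undercounts in one unlikely case, a true last dose the day before a new record starts (314 instead of 400 mg in the table).

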**Standardized Monthly IV Iron Dose (mg/month) from Week 28 to Week 52 (EP Average Monthly IV Iron Dose)**

- In order to calculate the average monthly IV iron dose from Week 28 to Week 52, the dose of IV iron will be standardized to obtain a continuous single unit IV iron dose in terms of mg/month for the period from the Week 28 visit date to the Week 52 visit date while the subject is on treatment.
  - Note: Subjects who are randomized but never treated or who permanently discontinue study treatment on or before the Week 28 visit date will not have a value for average monthly IV iron from Week 28 to Week 52.
- IV iron therapy concomitant medication records that occur or are ongoing during the period from the subject's Week 24 visit date to the Week 52 visit date will be selected and ordered by start date and end date.
- The standardization will be carried out with the following formula:
  - Standardized IV iron dose (mg/week) = IV iron drug dose (mg) \* frequency

Note: Frequency and Gap Factors defined as follows:

Frequency (from eCRF)	Frequency (for standardization formula)	Gap Factor
-----------------------	--	------------

CONFIDENTIAL

204837

**Iron Endpoints**

2 times per week	2	2.5 days
3 times per week	3	1.33 days
4 times per week	4	0.75 day
5 times per week	5	0.4 day
BID	14	0 days
Once daily	7	0 days
One time dose	1	n/a
Every 12 Hours	14	0 days
Every 2 weeks	0.5	13 days
Every 4 weeks	0.25	27 days
Once a month	0.23	29 days
Once a week	1	6 days
TID	21	0 days

- If the frequency of the record is not 'one time dose', then duration is calculated as follows:
  - If the concomitant medication record start date > earliest of (treatment stop date + 1 and Week 52 visit date), the duration of the record is 0.
  - If the concomitant medication record end date + gap factor < Week 28 visit date, the duration of the record is 0.
  - If the concomitant medication record end date + gap factor  $\geq$  Week 28 visit date or the record is ongoing, the duration of the record will be calculated as Stop Date – Start Date +1 day where:
    - Start date will be the latest of (concomitant medication record start date, and the Week 28 visit date).
    - Stop date will be the earliest of (concomitant medication record stop date + gap factor, treatment stop date + 1, and the Week 52 visit date).
- If the frequency of the record is 'one time dose', then:
  - If concomitant medication record start date < Week 28 visit date, or if earliest of (treatment stop date + 1 and Week 52 visit date) < concomitant medication record start date, then duration of the record is 0.
  - If Week 28 visit date  $\leq$  concomitant medication record start date  $\leq$  earliest of (treatment stop date + 1 and Week 52 visit date), then:
    - Frequency (for standardization formula) = 1
    - Duration = 7 days
- The total dose for each IV iron record will be: Standardized dose\*duration/7 days
- A weighted mean will then be used to obtain the monthly IV iron dose from Week 28 to Week 52:

$$\text{Mean monthly IV iron dose from Week 28 to Week 52 while on treatment} = \frac{[(\text{IV iron total dose}_{\text{Record 1}}) + \dots + (\text{IV iron total dose}_{\text{Record n}})]}{\{[\text{earliest of (treatment stop date + 1, Week 52 Visit Date)} - \text{Week 28 Visit Date} + 1]/30.4375 \text{ days}\}}$$

Iron Endpoints
Iron Use by Quarter

 
• The number and percentage of subjects in the following iron use categories defined by route will be summarized by quarters listed below for Average Quarterly IV Iron Dose: 
 
○ IV iron use only
 
○ Oral iron use only
 
○ Other iron use only
 
○ IV and oral iron use only
 
○ IV and other iron use only
 
○ Oral and other iron use only
 
○ IV, oral, and other iron use
 
○ No iron use
 
 
 
• When determining iron use by quarter, the gap factors mentioned in the IV iron standardization algorithm will also be applied to the end date for each iron record.
 
• Baseline iron use will also be included in summaries of iron use by quarter.
 

Average Quarterly IV Iron Dose

 
• The standardized IV iron (mg/month) dose will be summarized by quarters, where quarters will be defined using study visits as follows: 
 
○ Baseline
 
○ For summaries of on & off treatment IV iron dose: 
 
▪ Quarter 1 = [Randomization date – Week 12)
 
 
 
○ For summaries of on-treatment IV iron dose: 
 
▪ Quarter 1 = [Treatment start date + 1 – Week 12)
 
▪ Quarter 2 = [Week 12 – Week 24)
 
▪ Quarter 3 = [Week 24 – Week 36)
 
▪ Etc.
 
 
 
 
 
• To determine the planned start date and end date of quarters, the visit end date (from the SV domain) will be used. If there is not a corresponding visit, or if the subject is missing that visit, the planned visit date (Randomization date + 7*x) will be used, where x is the scheduled week (e.g., Week 24, x = 24).
 
• A subject's quarterly average IV iron dose will end at the earliest of the following: 
 
○ For summaries of on & off treatment IV iron dose: death date, study completion/withdrawal date, and the planned quarter end date.
 
○ For summaries of on-treatment IV iron dose: death date, study completion/withdrawal date, treatment stop date + 1, and the planned quarter end date.
 
 
 
• The standardization algorithm for IV iron described earlier in the table will be used to determine the standardized IV iron dose (mg/month) during each quarter.
 
• Standardized baseline IV iron dose will also be included in summaries of average quarterly IV iron dose.
 

CONFIDENTIAL

204837

Iron Endpoints
Reduction in IV Iron Supplementation

 
A reduction in IV iron supplementation relative to baseline occurs when Baseline average monthly IV iron > EP average monthly IV iron, when both baseline IV iron and EP average monthly IV iron are non-missing.
 

TIBC

 
TIBC will be calculated automatically by the central laboratory using: 
 
TIBC = UIBC + total iron
 
 
 

TSAT

 
TSAT will be calculated automatically by the central laboratory using: 
 
TSAT = 100 * (Serum Iron/TIBC)
 
 
 

Average Quarterly TSAT and Ferritin

 
The average TSAT and Ferritin values will be summarized by quarters, where quarters will be defined as they are for Average Quarterly IV Iron Dose, with the following exception: 
 
Baseline average quarterly ferritin and TSAT will take the average of all available records before or on randomization ferritin and TSAT values.
 
 
 
 
Note: any unscheduled values falling within these quarters will be used in the calculation of the quarterly average value.

Meeting Iron Management Criteria

Iron therapy will be administered if at any visit:
 
 
Ferritin <math>\leq</math> 100 ng/mL and/or TSAT <math>\leq</math> 20%
 
 
All iron must be stopped if at any visit:
 
 
Ferritin > 800 ng/mL and TSAT >20%, or
 
TSAT > 40%
 
 
Subjects meeting iron management criteria requiring starting and stopping of iron administration on the same day:
 
 
Ferritin <math>\leq</math> 100 ng/mL and TSAT > 40%
 

